- To assess the effect of a mHealth intervention or no intervention and/or metformin or placebo on WHO functional classification at week 12.
- To assess the effect of a mHealth intervention or no intervention and/or metformin or placebo on the average daily step count at week 12.
- To assess the effect of a mHealth intervention or no intervention and/or metformin or placebo on frequency of daily goal attainment at week 12.

- To assess the effect of a mHealth intervention or no intervention and/or metformin or placebo on daily aerobic time at week 12.
- To assess the effect of a mHealth intervention or no intervention and/or metformin or placebo on total daily activity at week 12.
- To assess the effect of a mHealth intervention or no intervention and/or metformin or placebo on resting heart rate at week 12.
- To assess the effect of a mHealth intervention or no intervention and/or metformin or placebo on HOMA-IR at week 12.
- To assess the effect of a mHealth intervention or no intervention and/or metformin or placebo on urine and plasma estradiol at week 12.
- To assess the effect of a mHealth intervention or no intervention and/or metformin or placebo on urine and plasma estrogen metabolites at week 12.
- To assess the effect of a mHealth intervention or no intervention and/or metformin or placebo on plasma lipid profiles at week 12.
- To assess the effect of a mHealth intervention or no intervention and/or metformin or placebo on plasma free fatty acid profiles at week 12.
- To assess the effect of a mHealth intervention or no intervention and/or metformin or placebo on plasma acylcarnitine profiles at week 12.
- To assess the effect of a mHealth intervention or no intervention and/or metformin or placebo on plasma BNP at week 12.
- To assess the effect of a mHealth intervention or no intervention and/or metformin or placebo on quadriceps skeletal muscle triglyceride content at week 12.
- To assess the effect of a mHealth intervention or no intervention and/or metformin or placebo on change in quadriceps skeletal muscle fatigue at week 12.
- To assess the effect of a mHealth intervention or no intervention and/or metformin or placebo on quadriceps skeletal muscle strength at week 12.

- To assess the effect of a mHealth intervention or no intervention and/or metformin or placebo on quadriceps skeletal muscle contractile tissue cross-sectional area at week 12.

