- Difference in plasma BNP between mHealth intervention or no intervention and/or metformin or placebo groups at week 12.
- Difference in quadriceps skeletal muscle triglyceride content between mHealth intervention or no intervention and/or metformin or placebo groups at week 12.
- Difference in change of quadriceps skeletal muscle fatigue between mHealth intervention or no intervention and/or metformin or placebo groups at week 12.
- Difference in quadriceps skeletal muscle strength between mHealth intervention or no intervention and/or metformin or placebo groups at week 12.
- Difference in quadriceps skeletal muscle contractile tissue cross-sectional area between mHealth intervention or no intervention and/or metformin or placebo groups at week 12.

- Difference in RV myocardial muscle triglyceride content between mHealth intervention or no intervention and/or metformin or placebo groups at week 12.
- Difference in tricuspid annular plane systolic excursion (TAPSE) between mHealth intervention or no intervention and/or metformin or placebo groups at week 12.
- Difference in RV and LV ejection fraction between mHealth intervention or no intervention and/or metformin or placebo groups at week 12.
- Difference in RV fractional area change between mHealth intervention or no intervention and/or metformin or placebo groups at week 12.
- Difference in tricuspid annular velocity (S') between mHealth intervention or no intervention and/or metformin or placebo groups at week 12.
- Difference in tricuspid regurgitant (TR) velocity between mHealth intervention or no intervention and/or metformin or placebo groups at week 12.
- Difference in estimated RV and RA pressure between mHealth intervention or no intervention and/or metformin or placebo groups at week 12.
- Difference in estimated RV and LV diastolic function between mHealth intervention or no intervention and/or metformin or placebo groups at week 12.
- Difference in RV free wall longitudinal strain between mHealth intervention or no intervention and/or metformin or placebo groups at week 12.
- Difference in screening clinical characteristics between responders and non-responders to mHealth intervention or no intervention and/or metformin or placebo groups at week 12.
- Difference in screening plasma metabolomics profiles, including all amino acids and lipidomics, between responders and non-responders to the mHealth intervention or no intervention and/or metformin or placebo groups at week 12.

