- Capacity of metabolomics profiles and clinical features at screening to predict response to the mHealth intervention or no intervention and/or metformin or placebo groups at week 12.

- Capacity of change in metabolomics profile and clinical features from screening to predict response to the mHealth intervention or no intervention and/or metformin or placebo groups at week 12.
- Difference in safety and tolerability between mHealth intervention or no intervention and/or metformin or placebo groups in PAH subjects over 12 weeks.
- Difference in fidelity of data collection and text transmission of the mHealth intervention over 12 weeks.
- Difference in patient satisfaction between mHealth intervention or no intervention and/or metformin or placebo groups at week 12.
- Difference in dropout rates between mHealth intervention or no intervention and/or metformin or placebo groups over 12 weeks.
- Difference in PAH-related hospitalizations between mHealth intervention or no intervention and/or metformin or placebo groups over 12 weeks.
- Difference in medication regimen escalation/reduction between mHealth intervention or no intervention and/or metformin or placebo groups over 12 weeks.
- Difference in incidence of death between mHealth intervention or no intervention and/or metformin or placebo groups over 12 weeks.

STUDY OBSERVATIONS:

- Subjects will be evaluated in person at screening (-2 weeks) and 12 weeks.
- Subjects will have telephone follow-up at weeks 1, 3, 6, and 9.
- HOMA-IR, estradiol and estrogen metabolites, lipid profiles, free fatty acids, acylcarnitine profiles, BNP levels, and other biomarkers will be assessed at screening and 12 weeks.
- Subjects will have six minute walk testing at screening and 12 weeks.
- Subjects will have a transthoracic echocardiogram at screening and 12 weeks.

- Subjects will answer quality of life questionnaires at screening and 12 weeks.
- Subjects at Vanderbilt will have cardiac and skeletal muscle MR spectroscopy screening and 12 weeks.
- Subjects at Vanderbilt will have muscle strength and function testing at screening and 12 weeks.

SAMPLE SIZE AND POWER:

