17. To determine whether mHealth, metformin, or both interventions combined affects plasma acylcarnitine profiles at week 12.
18. To determine whether mHealth, metformin, or both interventions combined affects plasma BNP at week 12.
19. To determine whether mHealth, metformin, or both interventions combined affects quadriceps skeletal muscle triglyceride content at week 12.
20. To determine whether mHealth, metformin, or both interventions combined affects change in quadriceps skeletal muscle fatigue at week 12.
21. To determine whether mHealth, metformin, or both interventions combined affects quadriceps skeletal muscle strength at week 12.

22. To determine whether mHealth, metformin, or both interventions combined affects quadriceps skeletal muscle contractile tissue cross-sectional area at week 12.
23. To determine whether mHealth, metformin, or both interventions combined affects RV myocardial muscle triglyceride content at week 12.
24. To determine whether mHealth, metformin, or both interventions combined affects tricuspid annular plane systolic excursion (TAPSE) at week 12.
25. To determine whether mHealth, metformin, or both interventions combined affects RV and LV ejection fraction at week 12.
26. To determine whether mHealth, metformin, or both interventions combined affects RV fractional area change at week 12.
27. To determine whether mHealth, metformin, or both interventions combined affects tricuspid annular velocity (S') at week 12.
28. To determine whether mHealth, metformin, or both interventions combined affects estimated RV and RA pressure at week 12.
29. To determine whether mHealth, metformin, or both interventions combined affects estimated RV and LV diastolic function at week 12.
30. To determine whether mHealth, metformin, or both interventions combined affects RV free wall longitudinal strain at week 12.
31. To determine screening clinical characteristics of responders and non-responders to mHealth, metformin, or both interventions combined at week 12.
32. To determine screening plasma metabolomics profiles, including all amino acids and lipidomics, of responders and non-responders to mHealth, metformin, or both interventions combined at week 12.
33. To determine whether metabolomics profiles and clinical features at screening predicts response to mHealth, metformin, or both interventions combined at week 12.

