1.8 Recruitment of Study Sample

Patients will be recruited from the Center for Pulmonary Vascular Disease (CPVD) at Vanderbilt University Medical Center (Nashville, TN), the Pulmonary Hypertension Clinic at Mayo Clinic (Rochester, MN), and the Pulmonary Hypertension Program at Cleveland Clinic (Cleveland, OH). Study sites may be contacting, communicating, and recruiting participants by, 1) telephone, 2) email using their assigned institution email address or, 3) through a secure patient portal and associated electronic medical record.

Potentially eligible subjects will be pre-screened and informed about that study to determine if they have an interest in enrolling. After the initial pre-screening, the subject will provide in-person informed consent or e-consent before any study procedures are performed.

1.9 ResearchMatch.org will also be utilized as a recruitment tool for this protocol. ResearchMatch.org is a national electronic, web-based recruitment tool that was created through the Clinical & Translational Science Awards Consortium in 2009 and is maintained at Vanderbilt University as an IRB-approved data repository (see IRB #090207).Inclusion/Exclusion Criteria

Inclusion criteria:

- Adults aged 18 or older.
- Diagnosed with idiopathic, heritable, connective tissue disease – associated PAH, or drug- or toxin-associated pulmonary arterial hypertension (PAH) according to World Health Organization consensus recommendations.
- Repaired simple congenital heart disease or unrepaired ASD
- Stable PAH-specific medication regimen for three months prior to enrollment. Subjects with only a single diuretic adjustment in the prior three months will be included. Adjustments in IV prostacyclin for side effect management are allowed.
- Subjects must own a Bluetooth capable modern smartphone capable of receiving and sending text messages and an active data plan.
- FEV1 > or = 60% predicted and no more than mild abnormalities on lung imaging
- WHO Functional Class I-III
- Ambulatory

Exclusion criteria:

- Prohibited from normal activity due to wheelchair bound status, bed bound status, reliance on a cane/walker, activity-limiting angina, activity-limiting osteoarthritis, or other condition that limits activity.
- Pregnancy
- Diagnosis of PAH etiology other than idiopathic, heritable, connective tissue disease – associated PAH, or associated with drugs or toxins
- Drug and toxin associated PAH patients with active drug use
- WHO Functional class IV heart failure

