1.22.8 Blood Biomarkers

a. HOMA-IR

Insulin resistance will be quantified using the homeostatic model assessment of insulin resistance (HOMA-IR), which estimates insulin resistance through fasting plasma insulin and glucose ratios, at screening and 12 weeks.

b. Lipid Metabolism

Altered lipid metabolism reflects insulin resistance. Fasting plasma lipid metabolites will be evaluated via non-targeted metabolomics screen. Mass spectroscopy of approximately 300 metabolites across all major metabolic pathways will be performed at screening and 12 weeks.

c. Fatty Acid Metabolism

Elevated circulating fatty acids and acylcarnitines contribute to RV lipotoxicity and indicate insulin resistance associated with pulmonary hypertension. To evaluate the effect of this intervention on fatty acid metabolism, we will measure fasting long-chain fatty acid and acylcarnitine profiles using mass spectrometry at screening and 12 weeks.

d. Plasma and Urine Estradiol and Estrogen Metabolites

Estrogen metabolites are associated with pulmonary hypertension in human PAH subjects. Estrogen metabolism we will be evaluated by measuring plasma estradiol (E2) and estrogen metabolites, including 2ME and 16 α OHE, using mass spectrometry at screening and 12 weeks.

e. Plasma NT-proBNP

Plasma NT-proBNP reflects right ventricular function in PAH and is a strong predictor of outcome in PAH. BNP will be assessed at screening and 12 weeks.

f. Amino Acids and Metabolomics

We and others have observed in cross-sectional studies that PAH is associated with insulin resistance and lipid abnormalities. Metabolites associated with insulin resistance and lipid metabolism have not been examined in the context of a clinical trial targeting insulin resistance. Changes in amino acids and metabolomic profiles with metformin and physical activity may provide insight into the mechanisms by which these interventions may improve insulin resistance (and outcomes) in patients with PAH.

g. Safety Labs

A comprehensive panel, complete blood count, hemoglobin A1c, and a urine pregnancy test will be assessed at screening and 12 weeks.

1.22.9 *Transthoracic Echocardiographic Measures*

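### The natriuretic-peptide secondary endpoint is named as BNP but scheduled as NT-proBNP, and the section that describes the measurement uses both names

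*Combined protocol and SAP*

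**What the plan says.** Five lists or summaries in the document use the name BNP:

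- The Protocol Summary objectives include "To assess the effect of a mHealth intervention or no intervention and/or metformin or placebo on plasma BNP at week 12". The secondary endpoint list in section 1.21 repeats this item.
- The Protocol Summary secondary endpoints give "Difference in plasma BNP between mHealth intervention or no intervention and/or metformin or placebo groups at week 12".
- Study Observations says "acylcarnitine profiles, BNP levels, and other biomarkers will be assessed at screening and 12 weeks".
- Secondary aim 18 in section 1.7 reads "To determine whether mHealth, metformin, or both interventions combined affects plasma BNP at week 12".

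Table 2 in section 1.20 has one natriuretic-peptide row. It is labelled NT-proBNP and marked at screening and at the week 12 visit.

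Section 1.22.8 e stands between the two. Its heading is NT-proBNP and its rationale says "Plasma NT-proBNP reflects right ventricular function in PAH and is a strong predictor of outcome in PAH". The next sentence is "BNP will be assessed at screening and 12 weeks".

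For analysis, section 1.24 sends continuous endpoints to a t-test, ANOVA or a rank test. It adds multivariable regression with baseline 6MWD, functional status, age and study site as example covariates. The endpoint's own screening value is not among the examples, and no transformation is mentioned.

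**The concern.** A secondary endpoint should identify one measurement. Here the endpoint lists point to one analyte and the schedule to another, and the section that should settle the matter gives a rationale for NT-proBNP and then says that BNP is measured. BNP and NT-proBNP are separate laboratory analytes whose values are not interchangeable. That is general laboratory knowledge; the plan gives no units or values for either.

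What is at stake is the integrity of one reported result. If the trial measures what Table 2 schedules, a result reported under the endpoint's stated name carries the wrong analyte label, and a result reported under the correct name departs from the endpoint as written. The rest of the document gives no basis for choosing, because no assay, laboratory or equivalence of terms is stated for this marker.

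**Working it through.** The plan gives no figure for this endpoint, so the check is a comparison of every place where the marker is named.

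| Place | Function | Analyte named |
|---|---|---|
| Protocol Summary, objectives | what is to be learned | BNP |
| Protocol Summary, secondary endpoints | endpoint definition | BNP |
| Protocol Summary, Study Observations | what is measured and when | BNP |
| Section 1.7, aim 18 | what is to be learned | BNP |
| Section 1.21, secondary list | endpoint list | BNP |
| Section 1.22.8 e, measurement sentence | what is measured and when | BNP |
| Section 1.22.8 e, heading and rationale | why it is measured | NT-proBNP |
| Section 1.20, Table 2 | what is measured and when | NT-proBNP |

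Three steps follow.

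1. **Is this a superseded text?** No. All eight entries are in the current body of the protocol, and the revision history does not mention a change of analyte.
2. **Do the entries conflict in function as well as in wording?** Yes. Three of them state what is measured and when. Study Observations and the 1.22.8 e sentence say BNP; Table 2 says NT-proBNP. So it is exact to say that the named endpoint is not the analyte in Table 2, and also that the prose contradicts Table 2.
3. **Does any other section resolve it?** Section 1.22.8 names mass spectrometry or spectroscopy for lipid metabolites, fatty acids and estrogens, but no method for this marker. Section 1.37 promises coordinating-center procedures for data collection at the sites, and section 1.50 refers to specimen storage in a single study laboratory. Neither mentions this analyte or says where it is assayed.

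Reach of the problem: section 1.7 numbers 41 secondary aims, and this is one of them. The sample size in section 1.26 rests on response rates of 40% and 73% for the composite primary endpoint. Recomputing it without continuity correction gives 35 per group, with power 0.809, which agrees with the plan. The natriuretic peptide does not enter that calculation.

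On the analysis, the screening value is already collected in every subject under Table 2. If ρ is the correlation between log screening and log week 12 values, adjusting for the screening value multiplies the residual variance by about 1 − ρ². The documents give no ρ, so no figure is put on the gain.

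**The case against.** The strongest reply is that BNP is loose shorthand. Table 2 applies to all three sites, it lists only NT-proBNP, and the heading and rationale of 1.22.8 e agree with it. That reading is plausible and is the reason for proposing NT-proBNP as the single name. It does not remove the inconsistency, because the document never says that the terms are equivalent and uses the other one in every objective and endpoint statement.

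Three stronger readings are tempting and are not supported.

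- **A subject could be measured by different assays at the two visits.** Section 1.19.4 requires the screening tests to be repeated at week 12, and Table 2 has one row marked at both visits. A switch would be a deviation, not something the plan allows.
- **The sites will pool unlike values, with a large loss of precision.** The text does not exclude this: section 1.19.1 lets some procedures take place at a site's own clinic, and no assay is fixed. It does not state it either, and sections 1.37 and 1.50 make it less likely. One can compute an inflation of pooled log variance, [s² + p(1 − p)(ln r)²] / s². Here r is the ratio of the two analytes, s the within-assay log SD and p the share of subjects on the other assay. With r = 3, s = 1.2, p = 1/3 it is (1.44 + 0.268)/1.44 = 1.19; with r = 10, s = 0.8, p = 1/2 it is (0.64 + 1.325)/0.64 = 3.07. Every input is assumed. If the assay differed by site, the study-site covariate in section 1.24 would absorb a constant shift on the log scale. These figures are therefore not offered as the size of the problem.
- **The result would be reported in the wrong units.** The plan gives no unit for either analyte. Only a wrong label can be claimed.

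It is also fair to say that the log-scale, baseline-adjusted analysis does not follow from a naming mismatch. It is a separate improvement. It is kept because the same sentences are being amended, the data already exist, and the covariate list in section 1.24 does not name the screening value.

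**Conclusion.** The inconsistency is certain from the text: the endpoint is defined as BNP, the schedule provides NT-proBNP, and section 1.22.8 e uses both. Its consequence is limited. If every site runs NT-proBNP as Table 2 directs, the harm is a mislabelled secondary endpoint. If sites run different analytes, the comparison would also mix unlike values, but that is a possibility left open by silence on the assay and cannot be sized from the documents. The conclusion assumes only that BNP and NT-proBNP are distinct analytes. The primary endpoint and the sample size are unaffected. This is worth correcting because it is clear and cheap, not because it threatens the trial's main result.

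**What to change.** 1. Name one analyte in the Protocol Summary objectives, endpoints and Study Observations, in aim 18, in the section 1.21 list and in the measurement sentence of 1.22.8 e. NT-proBNP is the natural choice, since it matches Table 2 and the heading and rationale of 1.22.8 e.
2. State in 1.22.8 e that the same assay is used at all three sites and at both visits, and that BNP and NT-proBNP values are not pooled.
3. State in section 1.24 that the week 12 value is analysed on the log scale by a linear model adjusted for the log screening value, in place of an unadjusted t-test or Wilcoxon test for this endpoint.

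The cost is an amendment to wording. No extra visit or blood draw is needed, since both samples are already scheduled. If a check of the laboratory records shows that more than one analyte has been run, the further cost is at most running stored plasma, where available, on one assay.

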We propose to test the hypothesis that interventions to improve insulin resistance will improve exercise capacity and WHO functional class in PAH. We propose three specific aims to test this 1) A prospective 2x2 factorial design 12-week clinical trial of metformin or placebo and activity intervention or usual care to assess effect on six minute walk and WHO functional class, 2) Assessment of the interventions in Aim 1 in a subset of patients on RV and peripheral muscle function and lipid content and markers of pulmonary vascular disease to define how these interventions may work in PAH and 3) Identify and prospectively test peripheral blood markers of metformin response in PAH. The broad goals of this work are to demonstrate the efficacy and mechanisms of interventions against insulin resistance in PAH and to identify which patients are most likely to benefit from these interventions, moving to precision medicine in PAH.

Background & Significance

1.1 Morbidity, mortality, and limitations of medical therapy in pulmonary arterial hypertension.

PAH is a highly morbid disease¹. Despite great progress in understanding disease mechanisms and nine FDA-approved drugs for PAH, contemporary data show that patients live on average 7 years after diagnosis^{1,2}. The six minute walk test (6MWT) distance has been used as a surrogate marker of drug efficacy in PAH, with a minimally important distance of about 33m³. Most drug therapy for PAH improves 6MWT distance approximately 30-40m⁴⁻⁸, indicating that current PAH therapies only modestly improve exercise capacity. Importantly, distance walked correlates directly with quality of life and mortality⁹⁻¹². Recent work has demonstrated a key role for insulin resistance in PAH²⁻⁶, but whether interventions against insulin resistance improve outcomes, such as six 6MWD or NYHA Functional Class (FC), is presently unknown. These data highlight the need for additional interventions to improve clinical outcomes in PAH.

1.2 Insulin resistance in PAH.

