1.6 Metformin in PAH

We have nearly completed an 8 week open label dose escalation (max dose 1g BID) study of metformin. Thus far we have enrolled 16 patients. There have been no serious adverse events thought related to the metformin exposure. One patient needed adjustment of diuretics and all patients have complained of mild diarrhea, with two requiring dose adjustment of metformin. Only one patient did not eventually reach the goal dose. In order to preserve the integrity of the study, we have not analyzed the primary endpoints aside from safety. In a preliminary review of MRS-quantified lipid content and found a numeric reduction in RV triglyceride content after treatment with metformin. These data suggest that RV lipid deposition may be reversed by metformin therapy and strongly support safety in a broad range of PAH patients with mild and severe disease.

Objectives and Specific Aims

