- To compare and define the screening plasma metabolomics profiles, including all amino acids and lipidomics, of responders and non-responders to mHealth intervention or no intervention and/or metformin at week 12.
- To assess the capacity of metabolomics profiles and clinical features at screening to predict response to the mHealth intervention or no intervention and/or metformin or placebo groups at week 12.
- To assess the capacity of change in metabolomics profile and clinical features from screening to predict response to the mHealth intervention or no intervention and/or metformin or placebo groups at week 12.
- To assess the effect of a mHealth intervention or no intervention and/or metformin or placebo on safety and tolerability in PAH subject over 12 weeks.
- To assess the fidelity of data collection and text transmission of a mHealth intervention over 12 weeks
- To assess the effect of a mHealth intervention or no intervention and/or metformin or placebo on patient satisfaction at week 12
- To assess the effect of a mHealth intervention or no intervention and/or metformin or placebo on dropout rates over 12 weeks.
- To assess the effect of a mHealth intervention or no intervention and/or metformin or placebo on PAH-related hospitalizations over 12 weeks.
- To assess the effect of a mHealth intervention or no intervention and/or metformin or placebo on medication regimen escalation/reduction over 12 weeks.
- To assess the effect of a mHealth intervention or no intervention and/or metformin or placebo on incidence of death over 12 weeks.

1.21.1 *Response to Therapy*

Response to therapy bot in will be classified as a binary yes or no response to therapy. A responder is defined by 10% or greater improvement in 6MWD over screening or improvement of at least one FC at week 12.

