Fatigue will be expressed as % drop in MVC during the fatigue protocol compared with the pre-fatigue MVC force. Recovery will be expressed as the % recovery of MVC force that was lost during the fatigue protocol at the 12 minute time point. Secondary analyses of force recovery will occur for the 3, 6, and 9 minute time points.

1.22.12 *Responders vs. Non-Responders.*

a. Definitions

Patients enrolled in our ongoing metformin pilot study will be divided into responders and nonresponders based on the primary endpoint of Aim 1. Clinical differences will be compared between groups, e.g. age, sex, BMI, PAH subtype, prevalent comorbidities, 6MWD, RV function and RV lipid content. Differences in molecular characteristics profiles will be compared between groups. Fasting plasma (before and after drug exposure) from our ongoing metformin pilot study will be used to perform metabolomic profiling via mass spectroscopy of approximately 300 metabolites across all major metabolic pathway, measuring all amino acids and including lipidomics.

b. Predictive Capacity

We will validate the metrics gathered from clinical and molecular characteristics of responders and non-responders. We will test predictive capacity in response to mHealth, metformin, or both interventions.

1.22.13 *Fidelity of Data Collection and Text Transmission*

In order to analyze the fidelity of the intervention, we will assess data collection and text transmission. Endpoints evaluating fidelity of data collection will be percent days with incomplete activity data and percent weeks with at least 6 days of activity data. The endpoint evaluating text transmission will be defined as percent total texts successfully delivered. Data for these endpoints will be gathered by the Fitbit Charge HR, transmitted to the subject's smartphone via Bluetooth, and then sent out to our mHealth platform via cellular network.

1.22.14 *Other Feasibility Endpoints*

- a. Drop Out Rates
- b. Patient Satisfaction: Patient satisfaction will be assessed using a customized survey developed for *A Mobile Health Intervention in Pulmonary Arterial Hypertension* trial and adapted for the PAH population.
- c. Side effects and tolerability of interventions including metformin.

1.22.15 *Medication Regimen Escalation/Reduction*

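### Aim 3 seeks markers of benefit, but its responder versus non-responder comparison cannot separate prognostic from predictive markers, and its change-score version does not exclude the variables that define response

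*Combined protocol and SAP*

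**What the plan says.** The Abstract words Aim 3 as "Identify and prospectively test peripheral blood markers of metformin response in PAH" and gives the broad purpose as "to identify which patients are most likely to benefit from these interventions, moving to precision medicine in PAH".

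Section 1.22.12 describes the method. Discovery comes first: "Patients enrolled in our ongoing metformin pilot study will be divided into responders and nonresponders based on the primary endpoint of Aim 1". Clinical features (an open-ended list of examples that includes 6MWD) and about 300 plasma metabolites are compared between the two groups. Validation follows: "We will test predictive capacity in response to mHealth, metformin, or both interventions". Section 1.6 describes the pilot: "We have nearly completed an 8 week open label dose escalation", with 16 patients enrolled so far and no control group mentioned.

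Response is judged against the patient's own screening value (section 1.21.1): "A responder is defined by 10% or greater improvement in 6MWD over screening or improvement of at least one FC at week 12".

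The Protocol Summary adds a change-score endpoint: "Capacity of change in metabolomics profile and clinical features from screening to predict response". That sentence goes on to name the mHealth, no-intervention, metformin and placebo groups. The objectives in section 1.21 and secondary aims 33 and 34 in section 1.7 cover the same ground, although the aims name only the interventions.

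Section 1.24 mentions an additive or synergistic effect of the two treatments. It contains no marker-by-treatment term.

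**The concern.** Which patients benefit is a question about effect modification: does the difference between active treatment and control depend on the marker? A comparison of responders with non-responders among treated patients answers another question: is the marker related to improving while on treatment? A marker that predicts improvement on every arm passes that comparison as readily as one that identifies a treatment effect.

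The plan itself expects 40% of placebo patients to respond. There is also a built-in example of a purely prognostic variable: WHO class I patients are eligible and cannot improve a class, so anything that tracks baseline class is tied to response on every arm.

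At stake is the precision-medicine claim. A marker of general improvement could be reported as a marker of metformin or mHealth benefit. If the change-score analysis took in change in 6MWD or class, its predictive performance would come partly or wholly from the definition of response.

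**Working it through.** **Inputs.** From section 1.26: placebo response 40%; active response built from 40% with a 10% gain in 6MWD, 50% with improved class and 17% with both; 35 per group. From section 1.22.12: about 300 metabolites. From section 1.6: 16 pilot patients so far. The documents give no figure for Aim 3 itself.

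**The plan's own figure.** 0.40 + 0.50 − 0.17 = 0.73. For 0.40 against 0.73, two-sided 0.05, 80% power and no continuity correction, the sample size is 35 per group (power 80.9%). The plan's figure is reproduced, and this point does not affect it.

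**Active-arm responders who would have responded on placebo.** The two response rates fix only a range.
- Upper end, if treatment turns no one into a non-responder: 0.40/0.73 = 55%.
- Lower end, with the least possible overlap: (0.40 + 0.73 − 1)/0.73 = 0.13/0.73 = 18%.

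**Can the comparison tell the two kinds of marker apart?** Simulation with 2,000 runs per row, 35 per arm, response 73% and 40%, and a normally distributed marker. The odds ratios per SD are assumptions. A prognostic marker has the same slope in both arms; a predictive marker has a slope only in the active arm. The within-arm test is a t-test of responders against non-responders in one active arm. The interaction test is the marker-by-treatment term in a logistic model of that arm and placebo.

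| Odds ratio per SD | Within-arm test, prognostic marker | Within-arm test, predictive marker | Interaction test, prognostic marker (false flag) | Interaction test, predictive marker (power) |
|---|---|---|---|---|
| 2 | 38% | 39% | 4% | 22% |
| 2.5 | 56% | 58% | 4% | 34% |
| 3 | 68% | 70% | 2% | 44% |

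Repeat runs move these by a few points: 34 to 70% for the within-arm columns and about 20 to 44% for interaction power. The second and third columns are practically the same, so the within-arm result carries no information on which kind of marker was found.

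**Using the factorial structure.** With marker-by-metformin tested across all four arms (35 each, assumed combination response 85%, marker active only with metformin), interaction power is 38%, 56% and 68% at odds ratios 2, 2.5 and 3. That is close to the within-arm detection rate, with false flags at about 4 to 5%.

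**Circularity, if the endpoint components are admitted.** For a yes/no component of the definition, specificity is 1 and AUC = (sensitivity + 1)/2.
- 10% gain in 6MWD: sensitivity 0.40/0.73 = 0.548, AUC 0.77.
- Class improvement: sensitivity 0.50/0.73 = 0.685, AUC 0.84.
- Both together: AUC 1.00.

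**Metabolite screen.** One unadjusted screen at 0.05 would pass 300 × 0.05 = 15 null metabolites. If the same null markers had to pass 0.05 in both the pilot and the trial, 300 × 0.05 × 0.05 = 0.75 would be expected. At 73% response, 16 pilot patients give about 12 responders and 4 non-responders (16 × 0.73 = 11.7).

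**The case against.** **Placebo is not ignored.** The Protocol Summary endpoints and the prediction objectives in section 1.21 name placebo groups. This stands. A reader might infer from section 1.22.12 that the placebo arm is left out of Aim 3, and the documents do not support that. What they lack is the contrast that would use it.

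**The comparison does not find prognostic markers only.** A reader might conclude that it finds prognostic markers instead of markers of benefit. The table shows otherwise: it picks up both at the same rate. The fault is that it cannot distinguish them.

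**The circularity is not written down.** 6MWD stands in a list of examples beside age, sex and BMI, which reads as a description of patients at entry. WHO class is not on that list, and no passage names change in either as a predictor. So it cannot be said that the plan uses the defining variables as predictors. It can be said that change in clinical features is a predictor and that nothing excludes them.

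**Pilot then trial is a two-stage design.** Testing pilot findings in separate data removes most chance findings, so 15 false markers is not a fair forecast for the whole programme. Replication does not remove prognostic markers, though, because they would replicate.

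**Proportion.** These are four of 41 secondary aims in a phase II trial. This also stands, and it limits the weight of the point.

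**Conclusion.** The concern holds in this form: the stated method cannot separate prognostic from predictive markers, and no marker-by-treatment analysis is specified, although the randomised placebo data for one will exist. Between 18% and 55% of active-arm responders would have responded on placebo. The 55% needs the assumption that treatment harms no one's response. At 35 per arm the within-arm comparison flags either kind of marker about 35 to 70% of the time, under assumed odds ratios of 2 to 3 per SD; smaller effects would give lower rates. The circularity is conditional: AUC 0.77, 0.84 or 1.00 applies only if the components are admitted, which the text neither states nor rules out. This is a cheap improvement. The primary endpoint, its analysis and the sample size are untouched.

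**What to change.** In section 1.22.12:

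1. Test markers in the randomised trial with a model of response on treatment, marker and marker-by-treatment, using all four arms including placebo. Call a marker predictive of benefit only on the interaction term, and label the analysis exploratory.
2. Keep the responder versus non-responder tables, in the pilot and in the trial, as descriptive.
3. Limit the interaction tests to markers selected in the pilot. Apply false-discovery control to any fresh screen of about 300 metabolites. Running Benjamini-Hochberg over 300 interaction tests would not be workable: at its first threshold (0.05/300) simulated power at 35 against 35 is 0 to 0.05% by Wald test and 1 to 4% by likelihood ratio.
4. Exclude change in 6MWD and change in WHO class from the change-score predictors, and report that analysis as an association.

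The cost is wording and a little analysis time. No new data are needed, since Table 2 already schedules metabolomics at screening and week 12. The downside is low interaction power (about 20 to 44% for one arm against placebo at the assumed odds ratios, higher when factorial arms are pooled), so few markers will be claimed.
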